## **Pediatric Data**

Preliminary data from 10 subjects of a Phase 1-2 study in pediatric patients with AML ages 2 to 16 years old indicated that decitabine PK parameters were consistent with known adult PK profiles.

### **1.1.4.2. Efficacy/Safety Studies**

#### **1.1.4.2.1. Efficacy of DACOGEN in Adult Subjects with Acute Myeloid Leukemia**

Study DACO-016 (CSR ref) was the largest randomized, active controlled, Phase 3 study in older ( $\geq 65$  years) patients with AML conducted to date with 485 subjects enrolled. The main objective was to compare DACOGEN, administered at a dose of  $20 \text{ mg/m}^2$  once daily for 5 consecutive days every 4 weeks (5-Day regimen), with Treatment Choice (TC) consisting of the subject's choice (with physician's advice) of the current standard care options of low-dose cytarabine ( $20 \text{ mg/m}^2$  once daily for 10 consecutive days every 4 weeks) or supportive care.

The primary analysis showed a clinically meaningful trend for improved OS for subjects treated with DACOGEN although it did not reach statistical significance. Subsequent analysis of survival data with one year of additional data showed a stronger treatment effect for DACOGEN. The median overall survival (OS) remained 5.0 months in the TC arm and 7.7 months in the DACOGEN arm with an improved hazard ratio of 0.82 (95% CI: 0.68, 0.99), and nominal  $p=0.0373$ . Results for other endpoints showed significant improvements for DACOGEN-treated subjects in response rates, PFS and EFS. These results were consistent with those obtained in the Phase2 study, DACO-017. Further details are provided in the IB.

### 1.1.4.2.2. Safety of DACOGEN in Adult Subjects with Acute Myeloid Leukemia

DACOGEN safety was evaluated using integrated datasets from the AML studies DACO-016 and DACO-017, 3-Day DACOGEN dosing in MDS studies D-0007 and EORTC-06011, and 5-Day dosing in MDS studies ID03-0180 and DACO-020 (See [Figure 2](#)). A total of 697 subjects treated with DACOGEN were evaluated for safety in clinical studies. The median duration of treatment with DACOGEN in subjects with AML was almost twice as long (4.14 months) compared with cytarabine treatment (2.35 months). Longer treatment duration for DACOGEN-treated subjects was a reflection of treatment benefit and tolerability.

The most frequently reported adverse events (AEs) in subjects treated with DACOGEN were myelosuppression (neutropenia, thrombocytopenia, and anemia) and consequences of myelosuppression (infections, bleeding events, and fatigue) which were reported at a higher (up to 15%) frequency compared with cytarabine treatment in subjects with AML ([Table 2](#)).

**Table 2: Most Frequently Reported Adverse Events in the Integrated AML Studies DACO-016 and DACO-017**

Preferred Term	Supportive Care	Cytarabine	DACOGEN
Pyrexia	21%	39%	48%
Thrombocytopenia	14%	40%	41%
Anaemia	14%	34%	38%
Nausea	17%	31%	33%
Febrile neutropenia	0%	26%	34%
Diarrhoea	17%	24%	31%
Neutropenia	3%	23%	32%

Note: Percentages were calculated with the number of subjects in each group as the denominator.

Note: Incidence was based on the number of subjects experiencing at least 1 adverse event, not the number of events.

Source: Summary of Clinical safety\Table18

The longer treatment duration led to a longer reporting period for adverse events for DACOGEN-treated subjects compared to cytarabine-treated subjects, and this should be considered in safety comparisons between these groups. In the supportive MDS studies, the median treatment duration was 7.34 months for the 5-Day studies and 5.65 months for the 3-Day studies. In all the DACOGEN treatment groups there were similar median dose intensities: in AML studies, 23.7 mg/m^2 per week, in MDS 5-Day studies, 21.2 mg/m^2 per week, and in MDS 3-Day studies, 21.1 mg/m^2 per week.

No new safety signals were identified in the AML studies compared with previous experience with DACOGEN in patients with MDS either in clinical studies or postmarketing experience. Further details of the safety of DACOGEN are provided in the IB.[11](#)

## 1.2. Combination Therapy

### Cytarabine

Study DACOGENAML2004 investigates the sequential administration of DACOGEN treatment followed by cytarabine. Cytarabine is indicated as an induction chemotherapy regimen for patients with AML and several other leukemias and lymphomas as a single agent or in combination with other antineoplastic agents. Cytarabine is a potent bone marrow suppressing agent resulting in hematological toxicities of cytopenias and anemia. Other

toxicities include gastrointestinal effects (nausea, vomiting, diarrhea, and anorexia), fever, alopecia, and neurotoxicity. For further information regarding cytarabine refer to the Summary of Product Characteristics (SmPC; <http://www.medicines.org.uk/EMC>), or the SmPC for cytarabine applicable to the local country.

Cytarabine is one of the most common agents used to treat AML and other hematological malignancies. Combinations of cytarabine are often used with other chemotherapeutic agents such as anthracyclines and results in response rates in the pediatric AML population of between 17% and 69%. Treatment of patients with AML after first or later relapse is confounded by the accumulating toxicity of certain chemotherapeutic agents such as the anthracyclines. Other combination therapies are needed to address this unmet need. The preclinical experiments described in Section 1.1.1 suggest that the sequential administration of DACOGEN and cytarabine may provide antileukemic activity in pediatric patients, hence cytarabine was chosen as the agent to be combined with DACOGEN for this study.

### 1.3. Overall Rationale for the Study

A significant proportion of pediatric AML patients relapses early or fails to respond to initial treatment. They require reinduction therapy with the ultimate aim of achieving a CR that would enable stem cell transplantation. The prognosis for a child with recurrent or progressive AML is generally poor. Approximately 50% to 60% of relapses occur within the first year following diagnosis, with most relapses occurring by 4 years from diagnosis.

Clinical and preclinical data suggest that sequential dosing of DACOGEN and cytarabine might be more effective than either agent used alone in refractory/relapsed pediatric AML. Preclinical data using human pediatric primary xenografts suggest the sequence of DACOGEN followed by cytarabine would be effective in patients with relapsed or refractory disease. Additionally, a Phase 1 study of epigenetic priming prior to treatment with standard “7 + 3” induction therapy showed that 20 mg/m^2 of DACOGEN could safely be given for 5 days prior to cytarabine (100 mg per day x 7 days) and daunorubicin (60 mg/m^2 per day x 2 days).

Despite commonality between the diagnosis and treatment of AML for children and adults there are significant differences between the diagnosis and treatment of children and adults. One of the principle challenges in investigating new approaches to treating pediatric patients is that they represent a very broad spectrum, from infants through to near adults. While in principle the treatment of younger children for example is no different to that of older individuals, the immaturity of organs in infants for example can confer a certain susceptibility to toxicity due to the differing pharmacokinetic and pharmacodynamic properties of certain drugs. In the case of cytarabine there is evidence to suggest that children younger than 2 years old may exhibit reduced cytarabine clearance.

The rational for this study is to examine the safety and efficacy of DACOGEN in sequential administration with cytarabine, which is the backbone of current standard combination treatments for relapsed/refractory pediatric AML. It is therefore necessary to first identify the dose of cytarabine that can be safely administered following DACOGEN treatment.

If the sequential combination can be safely administered with a clinically interesting level of activity, this would provide the basis for further evaluation in this indication.

## 2. OBJECTIVES AND HYPOTHESES

### 2.1. Objectives

#### Primary Objectives

The primary objectives of the Phase 1 portion of Study DACOGENAML2004 are:

- to determine the maximum tolerable dose (MTD) of cytarabine (up to  $2 \text{ g/m}^2$  per day x 5) that can be administered on Days 8-12 following treatment with DACOGEN  $20 \text{ mg/m}^2$  per day on Days 1-5 of a 28-day cycle.
- to determine PK parameters including maximum plasma concentration ( $C_{\max}$ ), Area under the concentration x time curve (AUC), time to maximum plasma concentration ( $t_{\max}$ ), and clearance (Cl) of decitabine on Day 5 of Cycle 1.

The primary objective of the Phase 2 portion of Study DACOGENAML2004 is to determine the response rate (CR + CRI) in children with relapsed or refractory AML when treated with DACOGEN  $20 \text{ mg/m}^2$  per day on Days 1-5 followed by cytarabine at the determined MTD on Days 8-12 for up to 4 cycles of treatment.

#### Secondary Objectives

The secondary objectives are to evaluate the safety profile of DACOGEN  $20 \text{ mg/m}^2$  per day administered on Days 1 to 5 followed by cytarabine on Days 8 to 12 for up to 4 cycles of therapy and to describe the duration of CR + CRI and evaluate the overall response (CR + CRI + PR) to treatment

Other objectives are to determine event-free survival (EFS) and overall survival (OS) for subjects treated with the sequential administration of DACOGEN and cytarabine, to explore the pharmacodynamic effects of DACOGEN with respect to DNA hypomethylation status and gene expression, and to explore predictive biomarkers for response to DACOGEN and cytarabine sequential treatment. The plasma PK profile of decitabine is a secondary endpoint in the Phase 2 portion of the study and levels of decitabine in the cerebrospinal fluid (CSF) will be evaluated if samples are collected as part of other required medical care.

### 2.2. Hypotheses

The hypothesis to be tested in the Phase 1 portion of this study is that DACOGEN administered at  $20 \text{ mg/m}^2$  per day for 5 consecutive days followed by at least  $1 \text{ g/m}^2$  per day (but not more than  $2 \text{ g/m}^2$  per day) of cytarabine on Days 8 to 12 can safely be given to children with relapsed or refractory AML.

The Phase 2 portion of the study is based on the hypothesis that the sequential administration of DACOGEN and cytarabine induces responses in pediatric patients with relapsed/refractory AML. It does not have formal hypothesis testing but is aimed to obtain initial efficacy and additional safety data of the sequential administration of DACOGEN and cytarabine.

### 3. STUDY DESIGN AND RATIONALE

#### 3.1. Overview of Study Design

This is an open-label, multicenter Phase 1-2 study to evaluate safety, PK, and clinical activity of DACOGEN in sequential administration with cytarabine in children ages 1 month to less than 18 years with relapsed or refractory AML. The study will determine the MTD of cytarabine that can be given on Days 8 to 12 following DACOGEN 20 mg/m^2 per day on Days 1 to 5 (Phase 1) and the response rate to this combination (Phase 2). Pharmacokinetic sampling will occur, at predetermined timepoints on Day 5 of Cycle 1 in the Phase 1 and the Phase 2 portion of the study.

##### 3.1.1. Phase 1 Portion of DACOGENAML2004

For the Phase 1 portion of the study, a “rolling 6” design is used. The total number of participants is dependent upon the number of cytarabine dose levels tested; the maximum number of which is 3 dose levels (1 g/m^2, 2 g/m^2, and 1.5 g/m^2) with a maximum of 18 evaluable subjects.

The MTD for cytarabine is based on the number of subjects experiencing a DLT by the end of Cycle 1. A non-hematological DLT is defined as: any Grade  $\geq 3$  toxicity that persists for  $>5$  days or any Grade 2 toxicity that persists for  $>7$  days and that is intolerable to the subject. A hematological DLT is defined as Grade 4 neutropenia or thrombocytopenia due to a hypoplastic bone marrow at Day 42, in the absence of malignant infiltration. The nominal duration of each cycle will be 28 days. However, patients who have not experienced bone marrow recovery at Day 28 will be followed up to Day 42. Failure of marrow recovery (improvement to Grade 3) by Day 42 will be considered a DLT. The maximum duration of Cycle 1 will therefore be 42 days.

The decision to dose escalate from the starting dose of 1 g/m^2 will be based on the number of subjects evaluable and the number pending evaluation during the first cycle. No dose escalation will occur unless a minimum of 3 subjects are fully evaluable with no dose limiting toxicity. If any additional subjects have been treated at that dose level, they must become evaluable before the dose can be escalated. The only exception is the setting in which 5 patients are evaluable, no DLT has been observed and data for one subject is incomplete making it impossible for the MTD to be exceeded. Further details of the “rolling-6” design and the determination of the MTD are provided in Section 6.3.

The decision to escalate or de-escalate dose levels and the identification of the MTD will be the responsibility of a Study Evaluation Team (SET) that will convene periodically based on the number of evaluable patients and the occurrence of dose limiting toxicities. The SET consists of the sponsor’s statistician and clinician and other members as needed, eg, clinical pharmacologist, safety physician. The SET will also include the lead investigator or designee from each country where the study is being conducted. Further description of the SET and their responsibilities is provided in Section 11.9.

Subjects receiving any dose level of cytarabine in the Phase 1 portion of the study may receive 4 cycles of study treatment unless the subject meets criteria for treatment discontinuation (Section 10.2). In adults with AML, the best response was observed after a median of 4 cycles of single-agent DACOGEN. Once the MTD of cytarabine is determined,

subjects treated at doses other than the MTD for less than 4 cycles can elect to proceed with remaining cycles at the MTD. The Phase 1 portion of the study will end when the MTD of cytarabine (no more than 2 g/m^2 per day x 5 days) administered on Days 8-12 in sequential administration with DACOGEN (20 mg/m^2 on Days 1-5) has been determined and all subjects have been treated for up to 4 cycles. Subjects who completed up to 4 cycles of the sequential treatment can elect to receive single-agent DACOGEN in the Continuation Phase of the study, if in the treating physician's opinion it would be beneficial. In order to use subject data efficiently and reduce the number of subjects in the study, data from the 6 (or fewer) subjects who are treated at the MTD level in the Phase 1 portion may be included in the Phase 2 portion of the study.

### **3.1.2. Phase 2 Portion of DACOGENAML2004**

The Phase 2 portion of the study will be an open-label, single arm study of the sequential administration of DACOGEN and cytarabine in at least 15 evaluable children with relapsed or refractory AML. Subjects who received the MTD of cytarabine for up to 4 cycles in the Phase 1 portion of the study and are evaluable will be included in the evaluation of the Phase 2 portion of the study. Subjects may elect to receive single-agent DACOGEN in the continuation portion of the study if, in the opinion of the treating physician, the subject would benefit.

The Phase 2 portion will utilize DACOGEN 20 mg/m^2 IV infusion over 1 hour on Days 1 to 5 and the dose of cytarabine determined in Phase 1 on Days 8-12. This regimen should be repeated for 4 cycles of treatment unless criteria for treatment discontinuation are reached.

There will be no independent data monitoring committee.

The primary efficacy endpoint will be the response rate, ie, CR + CRI (complete remission with incomplete blood cell count recovery) based on the evaluation up to the end of Cycle 4. Assessment of clinical response and disease progression will be conducted in accordance with the IWG response criteria. Bone marrow aspirates will be performed at the end of Cycle 1 of sequential treatment (Day 28 or within 8 days of the start of the next cycle), the end of Cycle 2 if the subject did not achieve a CR at the end on Cycle 1, at the end of sequential treatment, or at any time disease progression is suspected. Safety assessments will include adverse event monitoring, physical examinations, clinical laboratory parameter (hematology and chemistry) monitoring, and assessment of performance status, as described in the Time and Events schedule.

The clinical cut off for the primary endpoint will occur 30 days after the last subject has completed sequential treatment.

Blood samples will be drawn for the assessment of pharmacokinetic parameters. Blood samples will also be collected for biomarker analyses to explore pharmacodynamics effects of DACOGEN as well as potential predictive markers for response to DACOGEN + Cytarabine treatment. Biomarkers planned to be analyzed include DNA methylation, gene expression changes, gene methylation profiling, gene mutation profiling, and micro RNA profiling. Blast counts and other hematological parameters will be monitored by local laboratories. All study evaluations will be conducted according to the Time and Events Schedule.

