##### **Dose Limiting Toxicity (DLT) for Cytarabine**

For the Phase 1 portion of the study the primary endpoint will be DLT in the determination of the MTD (up to 2 g/m^2 per day) of cytarabine given on Days 8 to 12 following the administration of DACOGEN at 20 mg/m^2 on Days 1 to 5. DLTs are defined as the following

- Hematological DLT will be defined as failure to recover to an absolute neutrophil count (ANC) of  $0.5 \times 10^9/L$  (common terminology criteria for adverse events [CTCAE] Grade 3) and non-transfusion dependent platelet count of  $25 \times 10^9/L$  (CTCAE Grade 3) due to documented bone marrow aplasia/hypoplasia (malignant infiltration or other cause excluded), by Day 42. Bone marrow aplasia/hypoplasia is defined as overall marrow cellularity less than 25%.
- Non-hematological DLT is defined as: any Grade  $\geq 3$  toxicity possibly, probably or definitely related to study drug that persists for  $>5$  days; any Grade 2 toxicity that persists for  $>7$  days and that is intolerable to the patient.

The following events are more likely disease-related and, therefore, not considered DLTs:

- Grade 3 or 4 disseminated intravascular coagulation
- Grade 3 tumor lysis syndrome; grade 3 or 4 fever or grade 3 catheter-related infection, febrile neutropenia, infection, infection with unknown neutrophil count, and infection without neutropenia
- Grade 3 or 4 hypokalemia, hypomagnesemia, hyponatremia, or hypophosphatemia that is related to AML or administration of antifungal medications and is corrected with IV or oral supplementation.

Subjects who do not complete one treatment cycle and do not develop DLT will not be considered evaluable for DLT.

Decitabine PK parameters including  $C_{max}$ , AUC,  $t_{max}$ , and Cl will be determined from blood sampling on Day 5 of Cycle 1 and are a primary endpoint for the Phase 1 portion of the study.

#### Phase 2

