#### 9.5. Safety Evaluations

The evaluation period for safety will start from the time a signed consent/assent is provided. Toxicity/safety will be determined using National Cancer Institute common terminology criteria for adverse events (NCI-CTCAE) version 4.0.

The primary expected toxicity of cytarabine is severe myelosuppression. In addition rare cases of hypersensitivity and anaphylaxis have been reported after cytarabine dosing as well as “sudden respiratory arrest syndrome” occurring 6 to 12 hours after dosing and tumor lysis syndrome.

In addition to myelosuppression, administration of DACOGEN can cause peripheral edema, pallor, cardiac murmur and hypotension. Fever, fatigue, headache, lethargy and other CNS symptoms may occur. Cough, dyspnea, pneumonia and pharyngitis may be seen as well as mucositis and other side effects associated with myelosuppression and cellular cytotoxicity.

For the purposes of DLT evaluation, Cycle 1 will last until the start of Cycle 2, unless there is no recovery from toxicity within the specified time.

During the conduct of Phase 1 the SET will evaluate the tolerability of the combination until such times as a MTD for cytarabine can be agreed upon. Details regarding the SET are provided in Section 11.9.

During Phase 1, blood counts are to be monitored, but hematological parameters are not used to determine the MTD (ie, low blood counts per se are not considered to be dose-limiting toxicities or serious adverse events) because peripheral blood counts and bone marrow function are compromised in patients with relapsed leukemia. Hematological toxicity will only be assessed in responding patients who have grade 4 neutropenia ( $<0.5 \times 10^9/L$ ) or grade 4 thrombocytopenia ( $<25 \times 10^9/L$ ) due to a hypoplastic marrow at Day 42, in the absence of leukaemia.

During Phase 2 only myelosuppression events that are considered life threatening or result in an admission to hospital would be considered as serious adverse events.

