### **10.2. Discontinuation of Study Treatment (Sequential DACOGEN - cytarabine)**

If a subject's study treatment must be discontinued, the End of Sequential Treatment Visit should be performed however, this will not result in automatic withdrawal of the subject from the study. The subject may, at the discretion of the investigator, receive single agent DACOGEN in the Continuation Phase (see Section 9.1.5), otherwise the subject will enter the Follow-up Phase of the study. The End of Sequential Treatment/End of Treatment Visit and Follow-up visit assessments should be performed as specified in the Time and Events Schedule.

A subject's study treatment should be discontinued if:

- The subject experiences a DLT in the Phase 1 portion of the study
- The investigator believes that for safety reasons (eg, adverse event) it is in the best interest of the subject to discontinue study treatment
- The subject becomes pregnant
- The subject has progressive disease by IWG criteria
- The subject is non-compliant with regard to treatment visits
- The subject has sufficient clinical response, in the opinion of the investigator, to be eligible for transplant

- The subject starts another treatment regimen for AML
- The subject is unable to adhere to the study visit schedule or comply with protocol requirements
- The subject or subject's legal representative, parent, or guardian withdraws consent/assent for study treatment.

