### 11.3. Phase 1 Analysis

Subjects in the Phase 1 portion will be assessed for toxicity (DLT) to determine the recommended dose of cytarabine for the Phase 2 study.

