## 11.9. Study Evaluation Team

A Study Evaluation Team (SET) will be established to review the safety data of the Phase 1 portion of the study to determine dose escalation, dose de-escalation, and the MTD of cytarabine.

The SET consists of the sponsor's statistician and clinician (one of whom will chair the committee) and other members as needed, eg, clinical pharmacologist, safety physician. The SET will also include the lead investigator or designee from each country where the study is being conducted. The SET will convene regularly during the Phase 1 portion of this study to assess DLTs, determine dose escalation or de-escalation, and whether a MTD has been reached for cytarabine under these study conditions. The SET may convene at additional times for data review or any safety-related issues including during Phase 2. Any SET member has the right to request a SET meeting. A medical consultant may be asked to participate in the SET if deemed necessary in the interest of patient safety, upon request from the Sponsor or the investigator in preparation for SET meetings. Decisions on dose escalations or de-escalations, changes in the timing of PK or PD sampling, or other study conduct recommendations, will be made by the SET and documented.

All decisions made by the SET (eg, dose escalation/de-escalation, modification of the administration schedule or regimen) will be documented in a SET decision document and distributed to investigators. The IRB will be notified before implementation of any SET decision, if required. This document template will be provided in the sponsor's instruction manual and retained in the study master file and in the study center's files.

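### DLTs are counted only in Phase 1, and nothing obliges a toxicity review in Phase 2, so the DLT rate at the MTD rests on 5 or 6 children (as few as 3 at 1.0 g/m²)

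*Combined protocol and SAP*

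**What the plan says.** DLT belongs to Phase 1 throughout the protocol.

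- Endpoint (Section 9.2.2): "For the Phase 1 portion of the study the primary endpoint will be DLT in the determination of the MTD".
- Analysis (Section 11.3): "Subjects in the Phase 1 portion will be assessed for toxicity (DLT) to determine the recommended dose of cytarabine for the Phase 2 study".
- Grounds for stopping sequential treatment (Section 10.2): "The subject experiences a DLT in the Phase 1 portion of the study". No Phase 2 counterpart is listed.
- SET review, which Section 9.5 runs only until the dose is settled: "During the conduct of Phase 1 the SET will evaluate the tolerability of the combination until such times as a MTD for cytarabine can be" (the sentence closes with agreement on that dose).

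For Phase 2, Section 11.9 says: "The SET may convene at additional times for data review or any safety-related issues including during Phase 2". It also lets any SET member request a meeting and gives the team wide powers: "All decisions made by the SET (eg, dose escalation/de-escalation, modification of the administration schedule or regimen) will be documented in a SET decision document". Section 3.1.2 says: "There will be no independent data monitoring committee". No section gives a Phase 2 DLT count, a toxicity boundary or a scheduled Phase 2 safety review.

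Table 3 names 2.0 or 1.5 g/m² as the MTD only on 0/5 or at most 1/6 DLTs. Its note allows 1.0 g/m² to rest on as few as 3 evaluable subjects. Section 11.2 plans at least 15 evaluable Phase 2 subjects, counting those treated at the MTD in Phase 1.

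**The concern.** Five or six children are enough to choose a dose but not to describe its toxicity. The children who follow get the same first cycle at that dose, yet their DLT status is neither determined nor set against the Phase 1 result. If a level passed by chance, the evidence against it would build up in Phase 2 with no running count to show it and no rule requiring anyone to look.

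Serious adverse event reporting does not fully close the gap. Under Section 9.5, Phase 2 myelosuppression is serious only if it is life-threatening or leads to admission. Marrow hypoplasia without count recovery at Day 42, which is a DLT in Phase 1, need not surface that way.

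Also at stake is what the trial hands on. Section 1 makes a randomised Phase 3 study conditional on the combination being safe and effective, and Section 3.2 assigns Phase 2 the task of adding safety data. The toxicity measure that chose the dose would be reported only for the subjects used to choose it.

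**Working it through.** **Inputs.** Clearing rules: Table 3. Numbers at the MTD: Table 3 and Section 11.2. True DLT rates (p) are assumptions; the documents state neither a target nor an expected rate.

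**1. Method check.** The plan gives no operating characteristics for toxicity, so the method was checked on the efficacy figures in Table 5 (N=15). The Clopper-Pearson lower limit is the 2.5% quantile of Beta(x, n−x+1), and the upper limit is the 97.5% quantile of Beta(x+1, n−x). For 2/15 this gives 1.7% to 40.5%, as printed. For 4/15, P(X≥4 | 15, 0.20) and P(X≤4 | 15, 0.35) are both 35.2%, as printed. All seven rows agree.

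**2. Children at the MTD.** New evaluable children are 15−6=9 to 15−3=12, or 9 to 10 if the MTD is 2.0 or 1.5 g/m². Section 3.1.1 is looser on pooling ("data from the 6 (or fewer) subjects who are treated at the MTD level in the Phase 1 portion may be included") than Sections 3.1.2 and 11.2, which include these subjects outright. The 15 are evaluable for response, so the DLT-evaluable number may differ.

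**3. Chance that a level passes.** P(at most 1 in 6) = (1−p)^6 + 6p(1−p)^5. A 0/5 result passes whatever the sixth child would show, so it is already contained in this probability.

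- p=0.30: 0.118 + 0.303 = 0.42
- p=0.40: 0.047 + 0.187 = 0.23

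**4. Precision (exact 95% CI).**

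| DLTs/n | Observed | 95% CI |
|---|---|---|
| 0/3 | 0% | 0–70.8% |
| 0/5 | 0% | 0–52.2% |
| 1/6 | 16.7% | 0.4–64.1% |
| 2/15 | 13.3% | 1.7–40.5% |
| 3/15 | 20.0% | 4.3–48.1% |

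No count out of 15 equals 16.7%, so the two neighbours are shown. With 15 subjects the upper limit falls from 64.1% to between 40.5% and 48.1%.

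**5. Bias in the combined rate.** The Phase 1 subjects are there because their level passed. At p=0.40 their expected DLT count given at most 1/6 is 0.187/0.233 = 0.80. With 9 more children the combined expectation is (0.80 + 9×0.40)/15 = 4.4/15 = 29%, not 40%.

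**6. Illustration of a review trigger.** Suppose a SET review is obliged at 3 cumulative DLTs by subject 9, 4 by subject 12 or 5 by subject 15. Exact recursion over subjects 7 to 15, starting from at most 1/6:

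| True DLT rate | 15% | 20% | 30% | 40% | 50% |
|---|---|---|---|---|---|
| P(review obliged) | 0.05 | 0.12 | 0.31 | 0.56 | 0.77 |

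At 40%, about 0.10 of the 0.56 arises only at subjects 13 to 15. If the level passed on 0/5 instead, the figure at 40% is 0.43.

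**The case against.** A reader might infer that the MTD is fixed for good once Phase 1 ends and that nobody watches Phase 2. The documents do not support that. Any SET member can call a meeting, and the SET can de-escalate or change the regimen (Section 11.9). Serious adverse events reach the sponsor within 24 hours (Section 12.2.2). Cytarabine can be adjusted for toxicity (Section 6.3.1), and investigators can stop treatment for safety (Section 10.2). Safety is also a secondary endpoint, summarised by phase and combined where appropriate (Sections 9.2.2 and 11.8). So what rests on the few Phase 1 children is the DLT rate, not all safety knowledge. This stands and limits the point to a missing obligation and a missing tabulation.

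Two further readings go too far. Three subjects is not the general lower end; it applies only if 1.0 g/m² becomes the MTD after the higher levels fail. And 15 is the total at the MTD under Section 11.2, not the number added in Phase 2.

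Three objections concern the remedy, and each stands.

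- A plain pooled rate would flatter a bad dose (step 5).
- The data are not all in hand. Hematological DLT needs marrow evidence by Day 42, but the Time and Events footnote and Section 9.2.1 state that deadline for Phase 1 only. In Phase 2 the end-of-cycle marrow may fall within 8 days of a next cycle that can itself be delayed.
- The thresholds in step 6 have no basis in the documents, and the trigger is modest at a true rate of 30%.

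**Conclusion.** The point holds as a design gap, not as an error or contradiction. DLT classification ends with Phase 1, and no count or schedule obliges a safety review in Phase 2. With no independent committee, the optional SET meeting is the only collective review the protocol provides for.

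The size depends on assumed true DLT rates. At 30% to 40%, a level passes on 6 children with probability 0.42 to 0.23, and a result of 1/6 leaves rates up to 64.1% inside the interval. Using the further 9 or so children would narrow this usefully but not make it tight. The figures assume independent subjects, a common DLT rate across ages and phases, and about 15 DLT-evaluable children in total.

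A reader might also infer that an independent committee is required. Nothing here needs one: the SET already exists with the necessary powers.

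**What to change.** Amend Sections 11.3 and 11.9.

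1. **Classify.** Determine Cycle 1 DLT, by the study's own definition, for every subject who starts at the MTD, Phase 2 included. State how hematological DLT is classified when no marrow is available by Day 42.
2. **Oblige a review.** The sponsor prespecifies and justifies a cumulative DLT count at the MTD that obliges a SET review during Phase 2, and gives its operating characteristics as Table 5 does for response. What follows from the review stays with the SET. The thresholds in step 6 of the working are an illustration only.
3. **Report.** Give the DLT rate at the MTD with its exact 95% CI for the Phase 2-only subjects and for both phases combined. Note that the combined rate is biased low because the Phase 1 subjects were selected by the clearing rule.

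The cost is small. The SET exists, and adverse events, blood counts and an end-of-Cycle-1 marrow are already collected in Phase 2. What is added is some DLT classification, a statement on marrow timing and an occasional unneeded meeting: about 5% to 12% of trials at true rates of 15% to 20% in the illustration.
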